Subjects who commence on study will receive four quarterly structured, interdisciplinary home visits over 12 months from a team comprised of a movement disorders neurologist, social worker and nurse. At Visit 1, the nurse, social worker, and a member of the research team will travel to the home. The neurologist will be present via telemedicine. The home visit team will travel with an iPad and, after obtaining informed consent, connect to the neurologist via HIPAA-secure videoconferencing and begin the protocol-driven clinical activities and assessments in Figure 1 in the uploaded protocol. The nurse will conduct and, with the neurologist, score the UPDRS Motor Examination, reconcile medications, and complete a standardized home safety assessment. The social worker will obtain demographics, and administer the Multidimensional Caregiver Strain Index (MCSI) to the caregiver and the EuroQoL-5D (EQ5D) to both the patient and caregiver, respectively. The social worker will conduct a needs assessment of the dyad, including a discussion of goals of care. The team will administer the same survey that the usual care subjects will complete as a structured interview, as individuals in the home visit arm are expected to have more difficulty with dexterity and potentially cognitive issues, limiting the feasibility of completing the online survey unassisted. The survey will cover demographics, disease history, comorbidities, healthcare utilization, and unmet needs of the patient and caregiver. The team will probe for further details on necessary services or resources, and will ask specifically about areas of need in: education, resources, non-motor symptoms, psychiatric and palliative care, spiritual and/or religious support, and end-of-life planning. The team will create and counsel the dyad on a care plan. Within the Rush electronic medical record, the neurologist will enter orders and send a comprehensive, template-based note to the patient's healthcare providers. Visits 2-4 will be conducted at 4-month intervals and are identical except the social worker may join by telemedicine, depending on availability, and the queries on unmet needs will only be repeated at Visit 4.

The visits may be performed where the subject is residing at the time of scheduled visit (which could include but not restricted to the subject's home, nursing facility, hospital, etc.). The duration of the visits will be approximately 2.5-3 hours for Visit 1 and 1.5-2 hours for Visits 2-4.

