#### Characteristics of the Research Population

##### II.a. Number of Subjects

Total Number of Subjects in Home Visit and Usual Care arms: 85

Number of Subjects in Home Visit Arm: 25 subjects with Progressive supranuclear palsy, multiple system atrophy, corticobasal syndrome, or atypical parkinsonism. Participation in the home visit arm neither requires nor prohibits participation in the survey pilot phase.

Number of Subjects in Usual Care Arm: 60 subjects with Progressive supranuclear palsy, multiple system atrophy, corticobasal syndrome, or non-idiopathic PD atypical parkinsonism. Participation in the usual care arm neither requires nor prohibits participation in the survey pilot phase.

This is an exploratory study; no power analysis was conducted. The number of home visit subjects was projected based on recruitment to pilot work at NYU and discussions with Rush colleagues regarding feasibility. The number of control subjects was based on discussions with CurePSP senior staff regarding the size of their support group and social media-connected networks.

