##### II.d. Racial and Ethnic Origin

There will be no exclusion of subjects based on racial or ethnic characteristics. Study demographics are expected to match those of the population from which it was drawn. However, subjects must be fluent in English to participate in the Home Visit Program due to the general lack of appropriately translated

neurological and neuropsychological assessments and appropriate normative comparison samples. These factors are critical for accurate administration, scoring, and interpretation of neurological and neuropsychological test data.

II.e. Inclusion Criteria for All Subjects:

1. Each subject must be 40 years of age or older. A subject may be of either gender, any race/ethnicity.
2. Subjects will be those diagnosed with progressive supranuclear palsy, multiple system atrophy, corticobasal syndrome, Dementia with Lewy Bodies (DLB), or atypical parkinsonism without mention of idiopathic Parkinson's disease.
3. English speaking.

a. **Additional Inclusion Criteria For Home Visit Arm:**

- i. Each subject must *either* 1) be willing and able to provide written, informed consent for the study, and for whom capacity to consent will be assessed using the "Additional Inclusion Criteria for Home Visit Arm" document, or 2) if unable to provide informed consent due to lack of capacity, a caregiver is able to provide informed consent *and* the subject provides assent to participation.
- ii. Subjects must be homebound according to the Medicare definition: "Leaving your home isn't recommended because of your condition; your condition keeps you from leaving home without help (such as using a wheelchair or walker, needing special transportation, or getting help from another person); leaving home takes a considerable and taxing effort." (<http://www.medicare.gov/pubs/pdf/10969.pdf>)
- iii. Subjects reside in Chicago at the time of Visit 1.
- iv. The Subject must reside independently at the time of Visit 1.
- v. Subjects have one or more of the following criteria:
  - Fluctuation
  - Multi-morbidity
  - Mismanages medication
  - Cognitive impairment
  - Symptoms of depression and/or anxiety
  - High risk for re-hospitalization
  - High risk for nursing facility admission
  - Suspected elder abuse
  - Recent history of increased falls in home
  - Caregiver burnout suspected
- vi. Ability to participate in the research study as deemed by the Principal Investigator.

b. **Additional Inclusion Criteria for Usual Care Arm:**

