- a. Independent access to an internet-connected computer in order to complete online survey
- b. Valid email address

- c. Each subject must review and acknowledge their ability to provide informed consent for the study via the first screen of the online survey.

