##### V.b. Process of Consent

**Home visit subjects:** Subjects will be asked to carefully read the respective IRB-approved Informed Consent Form. The trained research study team member, will obtain consent in a private, distraction-free area in the patient's home. The person obtaining written informed consent from the subject will assess capacity to participate in the research study. It is not practicable to have an individual independent of the study team perform the capacity assessment or obtain informed consent because both are done in the potential subject's home, and both space and funding limit the number of individuals who can practically attend a visit.

Subjects who consent to be contacted about future studies will be notified of potential studies that they are eligible for as studies are available for recruitment. Their consent to participate in the CarePSP study does not apply to other studies. As such, subjects will have to go through the respective consent processes separately. Subjects have the right to refuse participation in any study without consequence to their participation in the registry or their routine patient care. Subjects will be informed about their right to request not to be contacted for specific periods of time or to discontinue active participation in the program, although their data will continue to be stored for future use.

**Usual care subjects:** We have incorporated the components of the informed consent document into the first page of the online survey. Potential subjects must read through the informed consent language on the first page and click a button agreeing to continue. On the next page of the survey, we have incorporated capacity assessment questions to ensure understanding of the consent process. Following correct completion of these questions, the potential subjects are then directed to the actual survey questions.

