Data management: The primary data will be entered into a HIPAA-compliant database (**REDCap**), with quarterly audits for fidelity. Data will be exported to Stata 14 for analysis.

Data analysis:

Descriptive statistics. We will describe the demographics, disease characteristics, QoL, and caregiver strain at baseline in patients and caregivers. Categorical variables will be summarized by frequencies and percentages. Continuous variables will be assessed for normality and summarized by mean and standard deviation, or median and interquartile range. Adequacy of matching will be evaluated using chi-square and *t*-tests.

Bivariate analyses. Change in EQ5D subscores and VAS over 1 year will be compared between groups, stratified by diagnosis, by two-sample *t*-test or nonparametric Wilcoxon rank sum test. If a subject dies or is lost to follow-up, the last values of the EQ5D will be carried forward. We will analyze the association with change in EQ5D for each demographic, confounder, and covariate via chi square or multivariate ANOVA, as appropriate. We will compare change in MCSI over 1 year by group, stratified by diagnosis; if lost to follow-up, the last MCSI value will be carried forward.

Multivariable analyses. We will construct a linear regression model with change in EQ5D domains and VAS as sequential dependent variables, and treatment status as the primary independent variable, stratifying by diagnosis. We will build complex models to assess the contributions of each significant covariate. Model building will include manual stepwise, backward elimination checking for multicollinearity and confounding. We will construct similar models wherein MCSI change is the dependent variable.

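### The home-visit arm is selected for advanced disease, but no homebound, motor or cognitive measure is described for controls, so the between-group model can adjust for stage only through weak proxies, and no matching step is described

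*SAP*

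**What the plan says.** **Home-visit arm (protocol II.e, additional criteria).** "Subjects must be homebound according to the Medicare definition", and each must also meet at least one of ten risk items. Patients without capacity can enter: "if unable to provide informed consent due to lack of capacity, a caregiver is able to provide informed consent", provided the patient assents. In addition, "The Subject must reside independently at the time of Visit 1".

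**Usual care arm (protocol II.e and V.b).** The added criteria are "Independent access to an internet-connected computer in order to complete online survey", an email address, and acknowledged ability to consent. A capacity check then precedes the survey: "Following correct completion of these questions, the potential subjects are then directed to the actual survey questions". No homebound or risk criterion applies, and V.b describes no surrogate route for controls.

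**Expected difference (protocol I.c).** The survey is given as an interview in the program arm because "individuals in the home visit arm are expected to have more difficulty with dexterity and potentially cognitive issues".

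**Measurements.** SAP, Other variables of interest, restricts UPDRS, Hoehn and Yahr and hallucinations to program patients. Appendix A lists short MoCA only in the home-visit rows. Controls give demographics, diagnosis, disease history, needs, resource use and EQ5D (protocol III, Usual care/controls). The SAP's confounder list is race, ethnicity, education, insurance, living situation, diagnosis, duration and comorbidities.

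**Analysis (SAP).** Under Descriptive statistics, "Adequacy of matching will be evaluated using chi-square and" *t*-tests. Under Multivariable analyses, change in EQ5D or MCSI is regressed on treatment status, stratified by diagnosis, with covariates chosen by backward elimination and a check for confounding.

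**The concern.** The two arms are drawn from different parts of the disease course by rule, not by chance. If rate of change over a year depends on stage, the treatment coefficient carries both the program's effect and the stage difference. A confounding check during model building can act only on variables recorded in both arms, and the direct stage measures described are recorded in one.

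The comparison with controls is part of hypotheses 1 and 2 (protocol I.a). Faster late-stage decline could hide a benefit; floor effects or regression to the mean could mimic one. The reference to matching adds a second risk: a reader of the results could take non-significant balance tests as evidence that the arms are comparable.

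**Working it through.** **1. The plan's own figure.** SAP, Power calculation, gives 42-63 patients for a VAS difference of 8.0-6.5 with SD 18, power 0.80 and two-sided alpha 0.05. A one-sample *t*-test calculation gives exactly 42 and 63. It concerns change in a single group and says nothing about comparability of the arms.

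**2. What is described in each arm.**

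| Aspect of stage | Home visit | Usual care |
|---|---|---|
| Homebound | Required, so all yes | Not described |
| Motor (UPDRS, Hoehn and Yahr) | Visits 1-4 | None described |
| Cognition (short MoCA) | Visits 1 and 4 | None described; capacity questions must be passed |
| Baseline EQ5D, resource use | Yes | Yes, but not listed as covariates |
| Diagnosis, duration, comorbidities | Yes | Yes |
| Living situation | Largely fixed by eligibility | Yes |

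Living situation is coded as home or nursing facility, so it cannot separate homebound from ambulatory people living at home.

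**3. Power of the balance tests.** Inputs are the enrolment figures: 20 vs 100 (SAP) and 25 vs 60 (protocol II.a). For a standardized imbalance s, noncentrality = s / √(1/n₁ + 1/n₂), two-sided 0.05.

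- 20 vs 100: √(1/20 + 1/100) = 0.245. s = 0.3 gives 1.22, power 23%; s = 0.5 gives 2.04, power 53%.
- 25 vs 60: √(1/25 + 1/60) = 0.238. s = 0.3 gives 1.26, power 24%; s = 0.5 gives 2.10, power 55%.
- Uncorrected chi-square, 50% vs 30%, exact enumeration: 41% at both sizes.

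A non-significant test would not show comparability.

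**4. Illustration of bias (assumed values, unadjusted contrast only).** Suppose homebound patients lose d extra VAS points a year and a share p of controls is homebound. The contrast is shifted by −(1 − p)d. With SD of change 18 (assumed; the SAP gives 18 beside a baseline mean) and 17 vs 80, SE = 18√(1/17 + 1/80) = 4.81.

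| d | p | Shift (points) | False significance, nominal 5% |
|---|---|---|---|
| 5-8 | 25-50% | 2.5-6.0 | 8-24% |
| 5-8 | 75% | 1.25-2.0 | 6-7% |
| 2-3 | 25-50% | 1.0-2.25 | 5.5-7.5% |

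The stated minimum important difference is 6.5-8.0. The result runs from negligible to serious depending on d and p, and neither document gives either value. The table also assumes that homebound patients decline faster, which is one of the possible directions.

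**5. What a homebound term would do.** Every treated patient is homebound, so treatment and homebound status form three cells: treated, homebound control, non-homebound control. A model with an intercept and both terms has three parameters and fits the three cell means exactly. Its treatment coefficient is the treated mean minus the homebound-control mean. Adding the term and restricting to homebound controls therefore give the same estimate; with further covariates, only their slopes can differ.

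**6. Precision of that estimate.** With k homebound controls, SE ratio = √(1/n₁ + 1/k) / √(1/n₁ + 1/n₂). The protocol's 25 and 60 become 21 and 48 after the SAP's 15% and 20% dropout.

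- 17 vs 80: k = 40, 20, 15, 10 gives +8%, +24%, +33%, +49%.
- 21 vs 48: k = 24, 12, 9, 6 gives +14%, +38%, +52%, +77%.

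**7. Cost of stratifying by diagnosis.** If the five diagnostic categories in II.e were evenly filled (assumed), 17 vs 80 leaves 3.4 treated per stratum, with SE 18√(5/17 + 5/80) = 10.7 points against 4.81 pooled.

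**The case against.** The strongest reply has four parts.

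- **Both arms do give functional data.** Baseline EQ5D covers mobility, self-care, usual activities and the VAS, and resource use is asked of both. This stands, and it supplies the cheapest repair. It is only partial: the items are self-reported, they are also the outcomes, and the SAP does not list them as covariates.
- **The survey is not reproduced.** Its disease-history or needs items may hold stage proxies. This also stands: the documents show only that no homebound, motor or cognitive measure is described for controls. A reader might infer that the model cannot separate program effect from stage at all; the documents do not support so strong a statement.
- **The model-building step may cope.** A reader might infer that backward elimination would discard a homebound term. In a simulation with an assumed rule (keep if p < 0.05 or the treatment estimate moves by more than 10%), the term was kept in 91-97% of runs, with mean bias within 0.1 point. The difficulty is that the variable is not described as collected, more than how it would be selected.
- **The study is exploratory.** The protocol states: "This is an exploratory study; no power analysis was conducted". The within-arm and unmet-needs aims do not depend on the control contrast. That limits the consequence, but the SAP still makes treatment status the primary independent variable.

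**Conclusion.** The point holds. By eligibility the arms differ in homebound status and in the route for patients without capacity, and the protocol itself expects worse dexterity and possibly worse cognition in the program arm. The adjustment available for stage is weak, and the phrase about matching has nothing behind it. The firm figures are the balance-test powers: 23-24% for 0.3 SD and 53-55% for 0.5 SD.

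The size and direction of the bias are unknown. It is tempting to conclude that stage would consume most of the 6.5-8.0 point difference. That needs assumed decline rates and homebound shares found in neither document, and it describes an unadjusted contrast rather than the planned regression. The conclusion about measurement rests on what the documents describe of the survey, not on the survey itself.

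**What to change.** 1. **Control survey.** Unless it already holds them, add the Medicare homebound questions at baseline and 12 months.
2. **SAP, Multivariable analyses.** Pre-specify one pooled between-group model with treatment, diagnosis and the baseline value of the outcome (EQ5D VAS or domain, or MCSI) as fixed terms. These use data already planned. Report beside it the comparison restricted to homebound controls, with their number. Do not present a homebound-adjusted model as a further check, since it is in effect the same estimate.
3. **SAP, Descriptive statistics.** Replace the matching tests with standardized mean differences labelled baseline comparability. Report how many home-visit patients enrolled by caregiver consent. State that the contrast is non-randomised and open to residual confounding by stage and cognition.

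**Cost.** Item 3 and the pooled model are changes of wording and reporting on planned data. Item 1 needs a few questions and an IRB amendment, and controls already surveyed would have no baseline answer. The restricted estimate has a wider interval, by the SE ratios in step 6 of the working; the number of homebound controls is not stated anywhere, so the actual cost is unknown. None of this removes the difference in cognition, which is why the caveat in item 3 is needed.

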The study team will provide one scheduled follow-up call at about 4 weeks post-visit (though this call

may occur as early as 2 or as late as 8 weeks after each visit, depending on the individual subject's circumstances and the ability of the study team to reach the patient and/or caregiver by phone). Change in quality of life and caregiver strain will be assessed over one year. The home visit cohort will be compared to a "usual care" cohort as measured by individuals with PRD living in the community who complete the online survey annually for 2 years covering demographics, disease history, quality of life, and caregiver strain.

Sixty (60) control participants will be recruited from the Rush University Parkinson's Disease and Movement Disorders Program, NYU Parkinson's Disease and Movement Disorders Institute, CurePSP (via social media postings), and from the CurePSP network of support group participants via in-person presentations from study staff, printed fliers, and emails. Control participants will be invited to complete an online version of the survey, created using REDCap research electronic data capture technology (HIPAA-secure database) housed at NYU. Caregivers of controls, when available, will also be invited to complete the online survey.

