Statistical Analysis Plan: In-Home Care for Patients with PSP and Related Disorders

NCT03552484

3-18-2019

Outcome ascertainment

Primary outcomes. The EQ5D will be completed at Visits 1-4 for program patients and annually for controls. This scale measures 5 domains of quality of life: *mobility, self care, usual activities, pain/discomfort, anxiety/depression*; each domain is scored from 1 to 5, with higher scores indicating better function. The scale also includes one item measuring overall self-rated health on a visual analogue scale (VAS) from 0 to 100, where 100 is “best health you can imagine”. This generic scale has been studied in PSP and related disorders and is available in an online format, supporting the feasibility of our control group. Change will be assessed in each EQ5D domain and in the VAS between baseline and 1 year. The instrument will also be administered at Visits 2 and 3 to avoid missing data if dyads are lost to follow-up prior to Visit 4. The MCSI will be completed at Visits 1-4 for caregivers, and annually for control caregivers. This scale is scored from 0-72, with 20-29 indicating moderate strain, 30 or higher indicating severe strain. MCSI scores will be evaluated as both continuous and categorical variables.

Demographics and confounders. include *race, ethnicity, education, insurance*, for patients and caregivers respectively; *living situation* (home or nursing facility), *diagnosis, diagnosis duration* (from year of onset or diagnosis, if onset unknown), and *comorbidities*.

Other variables of interest. The following items will be evaluated in program patients only: *hallucinations, motor severity (UPDRS, HY), and satisfaction* with the program (*Client Satisfaction Index-Short Form, CSI-SF*) administered to patients and caregivers.

Power calculation: Based on pilot recruitment, we anticipate enrolling 20 patients in home visits over 12 months, with a 15% drop out rate, yielding 17 patients at 12 months. We anticipate enrolling 100 control patients and 60 control caregivers, with a 20% drop out rate, yielding 80 patient and 48 caregiver controls. To detect a minimum clinically important difference of 6.5-8.0 in the EQ5D VAS, assuming a baseline mean of 37, standard deviation of 18, power of 0.80 and two-sided alpha of 0.05, we would require 42-63 patients.

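### The SAP tests the adequacy of a matching that the design does not contain, using p-values that cannot rule out moderate imbalance, and does not say whether the unadjusted or the adjusted comparison is the between-group result

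*SAP*

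**What the plan says.** **Balance check.** Under Data analysis, Descriptive statistics, the SAP states: "Adequacy of matching will be evaluated using chi-square and" t-tests. It gives no significance level for these tests and no consequence of passing or failing them.

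**How the groups arise.** Protocol section I.c draws controls from two clinics, CurePSP social media and support groups: "Control participants will be invited to complete an online version of the survey". Section II.a adds: "The number of control subjects was based on discussions with CurePSP senior staff". The additional criteria in section II.e require home visit patients to be homebound by the Medicare definition, to live in Chicago and to have at least one listed risk criterion. They require controls to have independent internet access and a valid email address. Section I.c itself expects home visit patients to have more difficulty with dexterity and possibly cognition.

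**Group comparison.** Under Bivariate analyses the SAP states: "Change in EQ5D subscores and VAS over 1 year will be compared between groups, stratified by diagnosis", by a two-sample t-test or a Wilcoxon rank sum test. MCSI change is also compared by group within diagnosis. Under Multivariable analyses it plans a linear regression of change on treatment status, again stratified by diagnosis. Significant covariates are carried into larger models, and these are reduced by manual stepwise backward elimination with a check for multicollinearity and confounding.

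**The concern.** Neither document gives a matching variable, a ratio or a procedure. The nearest wording, in protocol section II.d, says that study demographics should resemble those of the source population, which is not matching of controls to patients. The SAP therefore plans to test the success of a step that never happens, between groups whose entry rules pull in opposite directions.

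The check is also the wrong kind. A p-value mixes the size of an imbalance with the size of the groups. With 20 to 25 program patients, a moderate imbalance in a confounder can easily give a non-significant result, and a reader may take that as evidence that the groups are comparable.

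What is at stake is the between-group part of hypotheses 1 and 2 in protocol section I.a. This is a non-randomised comparison, so the adjusted and unadjusted estimates may differ materially. The plan leaves open which is the answer, and leaves the content of the adjusted model to be settled by the data.

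**Working it through.** **Is there a figure in the plan to reproduce?** None is attached to the balance check. The group sizes do reproduce. The SAP says "we anticipate enrolling 20 patients in home visits over 12 months, with a 15% drop out rate, yielding 17 patients at 12 months" (20 × 0.85 = 17) and "We anticipate enrolling 100 control patients and 60 control caregivers, with a 20% drop out rate, yielding 80 patient and 48 caregiver controls" (100 × 0.80 = 80; 60 × 0.80 = 48). The protocol has different sizes: "Number of Subjects in Home Visit Arm: 25 subjects" and "Number of Subjects in Usual Care Arm: 60 subjects". That difference needs reconciling separately. Both pairs are used here, at enrolled size, because balance is assessed at baseline.

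**Step 1. Detection by the t-test.** For a true standardised difference d, the test statistic is noncentral t with n1 + n2 − 2 degrees of freedom and noncentrality d / √(1/n1 + 1/n2). Two-sided 0.05 is assumed. The values of d are assumptions, shown as a range.

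- 20 v 100: √(1/20 + 1/100) = 0.245; critical t on 118 df = 1.98.
- 25 v 60: √(1/25 + 1/60) = 0.238; critical t on 83 df = 1.99.

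| True imbalance (SD) | Flagged, 20 v 100 | Flagged, 25 v 60 |
|---|---|---|
| 0.25 | 17% | 18% |
| 0.4 | 37% | 38% |
| 0.5 | 53% | 55% |
| 0.7 | 81% | 83% |
| 0.8 | 90% | 91% |

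For example, at 20 v 100 and d = 0.4 the noncentrality is 0.4 / 0.245 = 1.63, and detection is 37%. The chance of detection passes one half at about 0.48 SD (20 v 100) or 0.47 SD (25 v 60).

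**Step 2. Detection by chi-square.** A true difference of 50% v 35% (assumed) is flagged about 25% of the time at either pair of sizes. At 20 v 100, 50% v 30% is flagged about 41% of the time and 60% v 30% about 72%.

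**Step 3. Would a cutoff on standardised differences do better?** With no true difference, the standardised difference has a standard error of about 0.24 (Step 1). The chance of exceeding 0.25 in either direction is 2 × P(Z > 0.25/0.245) = 31% at 20 v 100, and 2 × P(Z > 0.25/0.238) = 29% at 25 v 60. A pass/fail rule at 0.25 would flag about 30% of balanced covariates. Standardised differences therefore belong in the table with intervals, as description.

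**Step 4. Why the baseline score matters.** Suppose equal SDs at both times, a baseline-to-1-year correlation ρ, and no other difference between the groups. A baseline imbalance B then shifts the comparison of change by (1 − ρ) × B in size. Take B = 0.5 SD = 9 VAS points, using the SAP's SD of 18 (given beside the baseline mean). The shift is 6.3 points at ρ = 0.3, 4.5 at ρ = 0.5 and 2.7 at ρ = 0.7. The SAP's target difference is 6.5 to 8.0 points. B and ρ are assumptions, so this shows only that the choice of model can matter on the scale of the target.

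**Step 5. What the regression can adjust for.** The SAP's Demographics and confounders paragraph lists race, ethnicity, education, insurance, living situation, diagnosis, diagnosis duration and comorbidities. The baseline EQ5D or MCSI score is not named as a covariate. Under Other variables of interest, motor severity and hallucinations are evaluated in program patients only. Homebound status is an entry requirement in one arm only.

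**The case against.** The strongest reply is that the SAP does not rest on a raw comparison. A reader who stopped at the bivariate paragraph might infer that it does. The next paragraph plans a regression with treatment status as the main independent variable for the EQ5D domains, the VAS and MCSI, and includes a check for confounding. The bivariate step is itself stratified by diagnosis, a listed confounder. This stands. The complaint is only that neither analysis is given precedence and that the regression's content is not fixed.

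Second, a reader might infer that the tests miss most imbalances, including large ones. The figures do not support that. Imbalances of 0.7 to 0.8 SD are flagged 81-91% of the time, and the opposing entry rules make large differences plausible.

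Third, a reader might infer that the trial would declare its groups matched and then skip adjustment. No rule in the SAP makes adjustment depend on the check. Nor is a clean sheet likely when several variables differ: six independent imbalances of 0.4 SD would all be missed with probability 0.633^6 = 6% (20 v 100) or 0.617^6 = 6% (25 v 60).

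Fourth, the protocol calls the study exploratory (section II.a). That lowers the stakes. It does not make the matching wording correct, and it does not tell a reader which estimate to rely on.

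**Conclusion.** The point holds in limited form. The SAP evaluates a matching that does not exist. Its significance tests flag imbalances of 0.25 to 0.5 SD only 17-55% of the time at the planned sizes, so a non-significant result cannot be read as balance. The plan also does not say which of two comparisons answers hypotheses 1 and 2, and it leaves the adjusted model to significance-driven selection without naming the baseline score.

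The detection figures assume a two-sided 0.05 level and approximately normal variables with equal variances. The sizes of imbalance are assumed, because the documents give none.

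A reader might want a single figure for the resulting bias or false-positive rate. The documents do not support one. It would need the number of unbalanced confounders, their gaps, their effects on change and the direction of each, as well as the SD of change. The documents give none of these.

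This should be changed before analysis. It does not invalidate the study.

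**What to change.** 1. Delete the sentence on adequacy of matching. In its place, report the standardised difference with its 95% interval for every baseline variable recorded in both arms, as description, with no p-values and no pass/fail cutoff.
2. State that the between-group result for hypotheses 1 and 2 is the adjusted estimate with its 95% confidence interval. Label the t-test or Wilcoxon comparison as descriptive.
3. Fix the model in advance: the baseline EQ5D or MCSI score, plus a named list drawn from the SAP's own confounders. Keep the list short enough for 17 to 25 program patients, and drop the stepwise elimination for this estimate.
4. State as limitations that motor severity (evaluated in program patients only) and homebound status (required in one arm only) cannot be adjusted for. Adjusting for the baseline score does not remove that confounding.

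The cost is SAP wording and one table column, with no new data and no change to care. The downside is that the headline estimate may be less favourable or less precise than the raw comparison.
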